3. METHODS

3.1 TRIAL DESIGN

The trial will be a 2 arm, parallel design, double blind RCT. The dietary intervention will span 6 months, consisting of an initial acute 2-month weight-loss driven by LED (Phase 1) and followed by a longer-term 4-month weight loss maintenance (Phase 2).

The 2 intervention arms are as follows:

[figure not shown]
1. Healthy diet/weight loss advice + feijoa whole fruit powder

Total meal replacement during the LED phase only (e.g. CID1-CID2), 4MJ/day; 1150 mg/d feijoa whole fruit powder daily in both phase 1 and phase 2 (to be consumed daily, with breakfast meal)

2. Healthy diet/weight loss advice + matched Placebo

Total meal replacement during the LED phase only (e.g. CID1-CID2), 4MJ/day; 1150 mg/d matched placebo (e.g. bland non active commercial placebo like microcrystalline cellulose) daily in both phase 1 and phase 2 (to be consumed daily, with breakfast meal)

FIGURE 1. INTERVENTION ARMS

▲ Fading visit design; clinical investigation days (CIDs) and group diet advice (combination of in-clinic and virtual/online sessions); LED - wks 0, 2, 4, 6, 8 (5 time points); Maintenance - mths 3, 4, 5, 6 (4 time points)

LED, low energy diet (4MJ/day): total meal replacement provided as sachets (Cambridge Weight Plan™ Ltd)

Body weight and composition (by dual energy x-ray absorptiometry, DXA) at CID 1/baseline, CID 2/end of LED, CID 3/4months & CID 4/end of study.

Magnetic resonance Imaging and Spectroscopy (MRI/MRS, sub-group, n=30; n= 15 placebo arm and n=15 whole fruit powder arm) assessment [7 day window] at CID 1/baseline, CID 2/end of LED, CID 4/end of study

Continuous glucose monitoring (CGM) over 4 days, for postprandial assessment incl. 2h OGTT and mixed (breakfast) meal tests; at CID 1/baseline all participants, CID 2/end of LED (sub-group; n= 40 placebo arm and n=40 whole fruit powder arm), CID 4/end of study (sub-group; n= 40 placebo arm and n=40 whole fruit powder arm)

[figure not shown]
Indirect calorimetry (IC) in a subgroup of n = 30 (n = 15 placebo arm and n = 15 whole fruit powder arm) measured during 2h OGTT at CID 1/baseline, CID 2/end of LED, CID 4/end of study

CHARACTERISATION OF BASELINE PHENOTYPE – IDENTIFYING PREDICTORS OF PPGR

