The postprandial CGM assessments will be conducted prior to the start of the LED, i.e. 3 days prior to CID1/baseline visit in all participants; and similarly 3 days prior to CID4/8 months but only in the sub-group of participants randomised to the placebo and the feijoa whole fruit powder intervention arms (40 participants each arm; Table 1).

WEIGHT LOSS_LOW ENERGY DIET [LED]: PHASE 1

Commercial LED meal replacements (Cambridge Weight Plan™ Ltd) will be consumed for 8 weeks throughout Phase 1. LED is energy restricted with a target intake of ~4MJ/day. The target macronutrient composition of the diet will be 15-20% of total energy from fat, 35-40% from protein and 45-50% from carbohydrate. LED products include shakes, soups, bars, porridge, pasta and savoury meals.

- Participants randomised to the Healthy diet/weight loss advice + feijoa whole fruit powder arm will receive the LED products to be consumed as a total meal replacement with the whole fruit powder to be supplemented into the diet and consumed alongside the LED, with target EI of 4MJ/day.
- Participants randomised to Healthy diet/weight loss advice + matched Placebo arm will receive the LED products to be consumed as a total meal replacement with the matched placebo to be supplemented into the diet and consumed alongside the LED, with target EI of 4MJ/day.

During Phase 1 participants will attend, either in person or via virtual online mHealth platform, 5 group meetings delivered from the HNU clinic site. At each group meeting, adverse events (AE) and concomitant medications will be recorded; and dietary advice and behavioural instructions provided by dietitians. Participants will be recommended to maintain PA as per baseline (no increase) during the LED weight-loss phase. All participants will remain on the LED until their CID2 visit at week 8. It is expected that weight loss over 8 weeks will be between 5-10% of baseline body weight.

WEIGHT MAINTENANCE_DIETARY INTERVENTION: PHASE 2

During Phase 2 (4 months) participants will attend, either in person or via virtual mHealth platform, 4 group meetings delivered from the research site. The dietary advice will adhere to the New Zealand Ministry of Health healthy eating guidelines (McIntyre & Dutton, 2015) for improving metabolic health, with diet advice provided by dietitians.

CLINIC ASSESSMENTS

TABLE 1. SUMMARY OF CID ASSESSMENTS OVER THE 6 MONTH STUDY PERIOD

Assessments	Phase 1 - LED		Phase 2- Maintenance	

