	CID1 M0	CID 2 M2	CID 3 M4	CID 4 M6
Demographics	X			
Height	X			
Body weight	X	X	X	X
Waist circumference	X	X	X	X
Blood pressure	X	X	X	X
Fasting blood sample	X	X	X	X
Concomitant medications	X	X	X	X
Adverse events	X	X	X	X
Questionnaires (e.g. QoL and *Bristol stool chart)	X *	X *	X	X *
DXA, body composition	X	X	X	X
MRI/MRS, pancreas & liver fat (subgroup, n = 30)	X (n=15 placebo + n=15 whole fruit powder arm)	X (n=15 placebo + n=15 whole fruit powder arm)		X (n=15 placebo + n=15 whole fruit powder arm)
Mixed meal tests (MMT) over 3 consecutive days, CGM; at home	X			X (subgroup; n=40 placebo + n=40 whole fruit powder intervention arm)
2-hr OGTT, CGM; in clinic	X	X (subgroup; n=40 placebo + n=40 whole fruit powder intervention arm)		X (subgroup; n=40 placebo + n=40 whole fruit powder intervention arm)
Physical activity/steps	X	X	X	X
Indirect calorimetry, IC (subgroup, n = 30)	X (subgroup; n=15 placebo + n=15 whole fruit powder intervention arm)	X (subgroup; n=15 placebo + n=15 whole fruit powder intervention arm)		X (subgroup; n=15 placebo + n=15 whole fruit powder intervention arm)
Diet diary, self-reported	X	X	X	X
24-h urine sample [N], diet compliance	X	X	X	X
Faecal sample collection	X	X		X

GROUP VISITS – a total of 9 group visits (Phase 1, LED: Week 0, 2, 4, 6, and 8; Phase 2, Maintenance: Month 3, 4, 5, and 6), combination of in person or via virtual mHealth platform will be conducted by dietitians throughout the intervention to provide dietary advice and support to maximise compliance and treatment success.

PARTICIPANTS

N = 80 per intervention group

Total sample size of 160 participants

INCLUSION

- Male and female
- Aged between 18 - 70 years
- BMI \geq 26 kg/m² and body weight \leq 150kg
- FPG in prediabetic range, 5.6 – 6.9 mmol/L
- Otherwise healthy, as per self-report
- Agreement to participate in a weight loss study

EXCLUSION

- Type 1 or type 2 diabetes mellitus
- Medications controlling glycaemia
- Current or history of significant disease including cardiovascular disease; pancreatic disease, or other digestive diseases including inflammatory bowel syndrome/disease, ulcerative colitis, Crohn's disease; cancer; plus associated medications including steroids (except topical steroids) and atypical antipsychotics in previous 3 months
- Recent body weight loss/gain > 10 % within previous 3 months or taking part in an active diet program; or current medications for weight loss; or intending to alter physical activity during following 12 months

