9.00 - 10.30am: blood sample every 15 min, $t = 15$ min to $t = 90$ min
10.45 am: final blood sample $t = 120$ min, cannula removed, IC stopped (canopy removed), body temperature & blood pressure

VISIT 4- CID 2/ MTH 2, END OF LED, START OF WEIGHT-MAINTENANCE (PHASE 2)

2 month end of LED assessment as outlined in Table 1, detailed methodologies as previously described. Including:

- DXA, body composition scan
- MRI/MRS scan for pancreas and liver fat assessment
- 4 day weighed food record/24-h diet recall
- 3 day PA assessment
- 2-hr OGTT in subgroup; n=40 placebo arm & n=40 whole fruit powder arm
- IC in subgroup; n=15 placebo arm & n=15 whole fruit powder arm
- Transition from LED to healthy diet/weight loss advice
- Collection of faecal sample for microbiome analysis
- Schedule virtual group advice visit at mth 3

VISIT 5 - CID 3/ MTH 4, DURING WEIGHT-MAINTENANCE (PHASE 2)

Assessments as outlined in Table 1. Including:

- 4 day weighed food record/24-h diet recall
- 3 day PA assessment
- Schedule virtual group advice visits for mths 5, 6

VISIT 6 - END OF STUDY ASSESSMENTS ['HOMEWORK']

Prior to CID 4/mth 6 end of trial, participants will repeat the series of pre-intervention assessments, during a 2-week window. Written and verbal instruction, including video call, will be provided to participants for each assessment. These will include:

- DXA, body composition scan
- MRI/MRS scan pancreas and liver fat assessment
- collection of faecal sample for microbiome analysis
- 4 day weighed food record/24-h diet recall
- 3 day MMT assessment (CGM inserted 3 days prior to CID 4) only in the whole fruit powder group
- 3 day PA assessment

Visit 7 - CID 4/MTH 6, END OF TRIAL

All participants will be fasted overnight prior to attending the study visit at the HNU. During the visit, the following will be conducted:

- Assessments as outlined in Table 1. Including:
- 2-hr OGTT in subgroup; n=40 placebo arm & n=40 whole fruit powder arm
- IC in subgroup; n=15 placebo arm & n=15 whole fruit powder arm
- Removal of CGM

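### The protocol contradicts itself on who has the month-6 mixed meal test: Visit 6 limits it to the powder arm, three other places give it to 40 participants per arm

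*Protocol*

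**What the plan says.** Four places in section 3 of the protocol say who has the MMT at the end of the study.

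- **Visit 6 (end-of-study homework):** "3 day MMT assessment (CGM inserted 3 days prior to CID 4) only in the whole fruit powder group". No sub-group size is given.
- **Table 1:** the row "Mixed meal tests (MMT) over 3 consecutive days, CGM; at home" has, in the month-6 column, "X (subgroup; n=40 placebo + n=40 whole fruit powder intervention arm".
- **Narrative on the timing of the CGM assessments** (just before the Phase 1 description): "only in the sub-group of participants randomised to the placebo and the feijoa whole fruit powder intervention arms (40 participants each arm; Table 1".
- **CGM text under Figure 1:** it describes "Continuous glucose monitoring (CGM) over 4 days, for postprandial assessment incl. 2h OGTT and mixed (breakfast) meal tests" and then assigns it at "CID 4/end of study (sub-group; n= 40 placebo arm and n=40 whole fruit powder arm".

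Section 3.1 also states "The trial will be a 2 arm, parallel design, double blind RCT". Under Outcome Variables, two-hour interstitial glucose from CGM is a secondary outcome with two components: (a) after the MMT and (b) after the oral glucose tolerance test (OGTT). Visit 7 keeps the month-6 OGTT in 40 participants of each arm. The co-primary outcomes are fasting plasma glucose (FPG) and body weight at 6 months.

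**The concern.** A rule that gives an outcome assessment to one arm only removes the randomised comparison for that outcome. Both arms go through the same 8-week low energy diet, with an expected loss of 5-10% of body weight, and then maintenance advice. A before-and-after change in MMT glucose in the powder arm alone would mix any feijoa effect with the diet, the weight loss and time.

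The second issue is blinding. To apply the Visit 6 line, whoever schedules the end-of-study homework must know the arm. Anyone aware of the rule could read a repeat MMT as a sign of feijoa. The test falls in the three days before CID 4, where FPG and body weight are measured.

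The line cannot be dismissed as an obvious slip. Visits 3, 4, 5 and 7 refer back to Table 1, but the Visit 6 text does not. The summary before the Background speaks of glucose-response algorithms after six months of feijoa consumption, so a powder-only repeat could be read as intended. The protocol does not say which text takes precedence.

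**Working it through.** **1. The four places side by side (month-6 MMT)**

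| Place | Placebo | Powder |
|---|---|---|
| Visit 6 | 0 | whole group, no limit stated (80 as randomised) |
| Table 1, MMT row | 40 | 40 |
| Narrative on CGM timing | 40 | 40 |
| CGM text under Figure 1 | 40 | 40 |

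Visit 6 disagrees with the other three on the placebo arm (0 against 40). Read literally, it also disagrees on the powder arm (no limit against 40).

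**2. What follows if Visit 6 is applied**

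The variance of a difference in means is SD² × (1/n₁ + 1/n₀). With n₀ = 0 no between-arm estimate exists, whatever n₁ is. This affects component (a) only. Component (b) keeps 40 against 40 under Visit 7 and Table 1.

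One caution on (b): the only month-6 CGM insertion step in the visit lists sits inside the powder-only bullet. However, Table 1 pairs CGM with the OGTT in both arms, Visit 7 lists CGM removal, and Visit 4 also gives no insertion step for its OGTT. This is a point to tidy, not evidence that (b) is lost.

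**3. The plan's own sample size, and whether it is touched**

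Inputs from Power Calculation: difference 0.3 mmol/L, SD 0.6 mmol/L, α = 0.05, power 80%, drop-out 20%. A two-sided test is assumed, since sidedness is not stated.

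- Standardised difference: 0.3 / 0.6 = 0.5.
- Normal approximation: n = 2 × (1.960 + 0.842)² / 0.5² = 62.8, so 63 per group.
- With the t distribution: 63.8, so 64 per group, as stated.
- Drop-out: 64 / (1 − 0.20) = 80 per group, as stated.

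The calculation reproduces. It concerns FPG and does not depend on the MMT.

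**4. What the 40-per-arm version could show**

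The protocol makes no power claim for the MMT. For context only, at 80% power and two-sided 0.05:

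- 40 against 40: (1.960 + 0.842) × √(2/40) = 0.63 SD (t-test 0.634).
- 32 against 32, assuming the trial's 20% drop-out also applies to the sub-group (40 × 0.80 = 32): 2.802 × √(2/32) = 0.70 SD (t-test 0.711).

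These figures describe the plan once corrected. They do not measure the defect.

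**5. Two separate mismatches on the same assessment**

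- The narrative dates the repeat "similarly 3 days prior to CID4/8 months but only in the sub-group of participants randomised to the placebo and the feijoa", and section 8 also uses an eight-month intervention period. The trial lasts 6 months and CID 4 is at month 6.
- The CGM text under Figure 1 includes meal tests in a description that also covers CID 2. Table 1 and Visit 4 list an OGTT at CID 2 but no MMT.

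**The case against.** The strongest reply is that three places agree on 40 per arm and one bullet does not. The reasonable reading is then a drafting error in Visit 6, not a decision to drop the placebo arm. That stands as far as it goes: a reader might infer that the design abandons the comparison and reveals allocation, but the documents do not support that as the settled plan. Both consequences arise only if staff follow Visit 6 over the other three places.

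Other parts of the reply also stand.

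- **Wearing a CGM would not identify the arm.** Table 1 pairs CGM with the OGTT for the placebo sub-group as well. Only the three test breakfasts would differ, and every participant has already eaten those at baseline.
- **A count of revealed allocations cannot be given.** One might infer that at least 40 participants would be unblinded. That assumes that participants, or staff dealing with them, know the rule, and Visit 6 gives no number.
- **The harm to the co-primaries is likely small.** They are laboratory glucose and body weight, and any inference would come at the end of the intervention.
- **The prediction objective is not lost.** Post-meal response is assessed by both OGTT and MMT, and the dietary intervention as defined includes the low energy diet. An algorithm predicting response to that whole package does not need feijoa separated from weight loss. Only a feijoa-specific claim does.

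What the reply does not remove is that a visit list is a working instruction, and this one conflicts with the schedule on who is tested.

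**Conclusion.** The concern holds as an internal contradiction with conditional consequences. The protocol gives two incompatible populations for the month-6 MMT. If Visit 6 is applied, placebo MMTs at month 6 fall from 40 to 0, one of the two components of a secondary outcome has no between-arm comparison, and scheduling is tied to allocation in a double-blind trial. If Table 1 is applied, none of this happens.

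The OGTT component, the co-primary outcomes and the sample size of 80 per group are unaffected. The conclusion rests on comparing the passages and needs no numerical assumption. The remark that FPG and body weight would be little affected is a judgement from the nature of those measures, not a calculation.

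The correction matters despite its limited reach, because placebo tests skipped at month 6 cannot be recovered and a revealed allocation cannot be undone. The eight-month label and the CID 2 mismatch are real but minor, and they do not bear on the restriction by arm.

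**What to change.** - Amend the Visit 6 bullet so that the three-day MMT is done in the CGM sub-group of both arms, 40 placebo and 40 powder, in line with Table 1, the Figure 1 text and the narrative. Scheduling must not depend on the arm or reveal it.
- State the CGM insertion before CID 4 for the same sub-group in both arms, so that the month-6 OGTT also has its sensor data.
- Separately, reconcile the eight-month references in the CGM narrative and section 8 with the 6-month schedule.
- Separately, reconcile the Figure 1 CGM text with Table 1 and Visit 4 on whether an MMT is done at CID 2.

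The main change is one line. The 40 placebo MMTs are already in Table 1, so it adds no procedure, no participants and no change to the sample size.

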4. ETHICS APPROVAL

Human ethics approval to conduct this study will be obtained from the Auckland Health and Disabilities Committee (HDEC), Auckland, New Zealand.

5. TRIAL REGISTRATION

The trial will be registered with the Australia New Zealand Clinical Trials Registry (ANZCTR).

6. RISKS AND BENEFITS

Collection of blood samples is done by venous cannulation, which may result in mild discomfort for the participant. The participant will be monitored by a research nurse throughout the day and no adverse events are expected. Participants will be continuously monitored at all study visits and following the visits by telephone interview, over the study period, by the research staff.

DXA uses a low dose of ionizing radiation, similar to the natural radiation exposure of a 1-hr aeroplane flight, e.g. from Auckland to Wellington. The exposure to participants represents a very low risk. We do not foresee any safety concerns with regards to cumulative radiation exposure with this frequency of DXA scans. Natural background radiation is approximately 2.4 mSv a year or 6.7 μ Sv a day; a whole-body DEXA scan gives the equivalent radiation dose of 1 day or less (Bazzocchi, Ponti, Albinini, Battista, & Guglielmi, 2016). Pregnancy in female participants is an exclusion criteria, as is metal implants such as cardiac pacemakers.

7. DATA COLLECTION/PRIVACY/CONFIDENTIALITY

Data will be de-identified and recorded in hard copy on case report forms (CRF) and also stored in electronic format using Microsoft Excel. All hard copy CRFs will be stored in secure locked cabinets and the electronic data stored on a secure server with an automatic backup facility at the University of Auckland Human Nutrition Unit.

Data will be de-identified and recorded using the case report form (CRF) platform Redcap (<https://projectredcap.org/>), in addition to hard copy CRFs and also stored in electronic format using Microsoft Excel, with password protection. All hard copy CRFs will be stored in secure locked cabinets and the electronic data stored on a secure server with an automatic backup facility at the University of Auckland Human Nutrition Unit, AgResearch, Plant and Food Research and the Malaghan Institute.

8. ADVERSE EVENT REPORTING

Adverse events (AEs) are classified as serious or non-serious. The investigator is responsible for reporting and recording adverse events. An adverse event is defined as an event that is undesirable occurring in a participant, whether related or unrelated to the study procedure.

Serious adverse events (SAEs) include:

- Death.
- Life threatening event.
- Serious injury i.e. events which require hospitalisation or medical attention.

Non serious events include:

- All events not defined as serious.

Any reported AEs and SAEs will be recorded throughout the 8 mth intervention period.

9. DATA RETENTION

All data will be retained for a period of 10 years, or as stipulated by the NZ National Human Ethics Committee (HDEC).

10. CLINICAL TRIAL SITES

The study will be conducted at the Human Nutrition Unit, University of Auckland, with body composition assessments conducted at the Clinical Research Centre and the Centre for Advance MRI at the Faculty of Health and Medical Sciences, University of Auckland.

11. APPENDICES

[figure not shown]
APPENDIX: FINDRISC FORM FOR PRESCREEN ASSESSMENT OF PREDIABETES

 Finnish Diabetes Association

TYPE 2 DIABETES RISK ASSESSMENT FORM

Circle the right alternative and add up your points.

1. Age
 
0 p. Under 45 years 2 p. 45–54 years 3 p. 55–64 years 4 p. Over 64 years
 
2. Body-mass index (See reverse of form)
 
0 p. Lower than 25 kg/m² 1 p. 25–30 kg/m² 3 p. Higher than 30 kg/m²
 
3. Waist circumference measured below the ribs (usually at the level of the navel)
 
 
 MEN	WOMEN	
 
 0 p. Less than 94 cm	Less than 80 cm	
 
 3 p. 94–102 cm	80–88 cm	
 
 4 p. More than 102 cm	More than 88 cm	
 
	MEN	WOMEN	0 p. Less than 94 cm	Less than 80 cm	3 p. 94–102 cm	80–88 cm	4 p. More than 102 cm	More than 88 cm	
6. Have you ever taken medication for high blood pressure on regular basis?
 
0 p. No 2 p. Yes
 
7. Have you ever been found to have high blood glucose (eg in a health examination, during an illness, during pregnancy)?
 
0 p. No 5 p. Yes
 
8. Have any of the members of your immediate family or other relatives been diagnosed with diabetes (type 1 or type 2)?
 
0 p. No 3 p. Yes: grandparent, aunt, uncle or first cousin (but no own parent, brother, sister or child) 5 p. Yes: parent, brother, sister or own child

MEN	WOMEN								
0 p. Less than 94 cm	Less than 80 cm								
3 p. 94–102 cm	80–88 cm								
4 p. More than 102 cm	More than 88 cm								


4. Do you usually have daily at least 30 minutes of physical activity at work and/or during leisure time (including normal daily activity)?
 
0 p. Yes 2 p. No
 
5. How often do you eat vegetables, fruit or berries?
 
0 p. Every day 1 p. Not every day
	
 
Total Risk Score
 
 The risk of developing type 2 diabetes within 10 years is
 
 
 Lower than 7	Low: estimated 1 in 100 will develop disease	
 
 7–11	Slightly elevated: estimated 1 in 25 will develop disease	
 
 12–14	Moderate: estimated 1 in 6 will develop disease	
 
 15–20	High: estimated 1 in 3 will develop disease	
 
 Higher than 20	Very high: estimated 1 in 2 will develop disease	
 
 
 
Please turn over
	Lower than 7	Low: estimated 1 in 100 will develop disease	7–11	Slightly elevated: estimated 1 in 25 will develop disease	12–14	Moderate: estimated 1 in 6 will develop disease	15–20	High: estimated 1 in 3 will develop disease	Higher than 20	Very high: estimated 1 in 2 will develop disease
Lower than 7	Low: estimated 1 in 100 will develop disease										
7–11	Slightly elevated: estimated 1 in 25 will develop disease										
12–14	Moderate: estimated 1 in 6 will develop disease										
15–20	High: estimated 1 in 3 will develop disease										
Higher than 20	Very high: estimated 1 in 2 will develop disease										

	Yes, limited a lot	Yes, limited a little	No, not limited at all		
i. Walking one hundred yards wlkoyd	1 	2 	3 		
j. Bathing or dressing yourself bthdrs	1 	2 	3 		
4. During the past 4 weeks, how much of the time have you had any of the following problems with your work or other regular daily activities as a result of your physical health ?					
	All of the time	Most of the time	Some of the time	A little of the time	None of the time
a. Cut down on the amount of time you spent on work or other activities cuttm	1 	2 	3 	4 	5 
b. Accomplished less than you would have liked dolss	1 	2 	3 	4 	5 
c. Were limited in the kind of work or other activities lmtknd	1 	2 	3 	4 	5 
d. Had difficulty performing the work or other activities (for example, it took extra effort) dffwrk	1 	2 	3 	4 	5 
5. During the past 4 weeks, how much of the time have you had any of the following problems with your work or other regular daily activities as a result of any emotional problems (such as feeling depressed or anxious)?					
	All of the time	Most of the time	Some of the time	A little of the time	None of the time
a. Cut down the amount of time you spent on work or other activities ecuttm	1 	2 	3 	4 	5 
b. Accomplished less than you would like edolss	1 	2 	3 	4 	5 
c. Did your work or activities less carefully than usual elsscr	1 	2 	3 	4 	5 
6. During the past 4 weeks, to what extent has your physical health or emotional problems interfered with your normal social activities with family, friends, neighbors, or groups? extent					
Not at all	Slightly	Moderately	Quite a bit	Extremely	
1 	2 	3 	4 	5 	

7. How much bodily pain have you had during the past 4 weeks? pnxtnt						
None 1 	Very mild 2 	Mild 3 	Moderate 4 	Severe 5 	Very severe 6 	
8. During the past 4 weeks, how much did pain interfere with your normal work (including both work outside the home and housework)? pnintf						
Not at all 1 	Slightly 2 	Moderately 3 	Quite a bit 4 	Extremely 5 		
9. These questions are about how you feel and how things have been with you during the past 4 weeks. For each question, please give the one answer that comes closest to the way you have been feeling.						
How much of the time during the Past 4 weeks....		All of the time	Most of the time	Some of the time	A little of the time	None of the time
a. Did you feel full of life? flife		1 	2 	3 	4 	5 
b. Have you been very nervous? nervs		1 	2 	3 	4 	5 
c. Have you felt so down in the dumps that nothing could cheer you up? edown		1 	2 	3 	4 	5 
d. Have you felt calm and peaceful? ecalm		1 	2 	3 	4 	5 
e. Did you have a lot of energy? fenrqy		1 	2 	3 	4 	5 
f. Have you felt downhearted and depressed? edprss		1 	2 	3 	4 	5 
g. Did you feel worn out? wrnout		1 	2 	3 	4 	5 
h. Have you been happy? ehppy		1 	2 	3 	4 	5 
i. Did you feel tired? etred		1 	2 	3 	4 	5 
10. During the past 4 weeks, how much of the time has your physical health or emotional problems interfered with your social activities (like visiting with friends, relatives, etc.)? sinterf						
	All of the time 1 	Most of the time 2 	Some of the time 3 	A little of the time 4 	None of the time 5 	

11. How TRUE or FALSE is each of the following statements for you?					
	Definitely True	Mostly True	Don't Know	Mostly False	Definitely False
a. I seem to get sick a little easier than other people esysck	1 	2 	3 	4 	5 
b. I am as healthy as anybody I know hlthy	1 	2 	3 	4 	5 
c. I expect my health to get worse hlthwrs	1 	2 	3 	4 	5 
d. My health is excellent hlthgd	1 	2 	3 	4 	5 

